13.5. Data Monitoring Committee

Since the study will include subjects with the age of 16 years and older an independent Data Monitoring Committee (DMC/DSMB) will review all adverse events and all serious adverse events during the whole study period. The DMC/DSMB will review all adverse events that may occur after the first two subject have been treated. The DMC will provide a recommendation of continuation of the study. The third and fourth subject could be included 1 week after the first two subject have been treated with pedicle screws. The DMC/DSMB will review again and will provide a recommendation of continuation of the study. The DMC/DSMB will have regular meetings to evaluate any kind of events and provide recommendations regarding continuation of the study.

14. EARLY TERMINATION OR SUSPENSION OF THE CLINICAL INVESTIGATION

There are no provisions or interim analyses planned that can result in an early termination of the trial. Any signs of unknown or increased risks for the subjects will be discussed by the sponsor and investigator to assess the impact on the subjects and clinical investigation. Serious or repetitive occurrence of deviations from study protocol or non-compliance with regulations may also be reason for early termination or suspension of a study site.

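### Does Section 14 of the protocol, which denies any planned provision for early termination, contradict the DMC's role in Section 13.5?

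*Protocol*

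**What the plan says.** Protocol Section 14 (early termination or suspension) begins: "There are no provisions or interim analyses planned that can result in an early termination of the trial." On emerging risk, its next sentence reads: "Any signs of unknown or increased risks for the subjects will be discussed by the sponsor and investigator", with the aim of judging the effect on the subjects and on the investigation. Its last sentence adds that serious or repeated protocol deviations, or regulatory non-compliance, may also lead to a study site being ended or suspended. The DMC is not named in this section.

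Protocol Section 13.5 gives the inclusion of subjects from age 16 as the reason for a DMC, and says that "an independent Data Monitoring Committee (DMC/DSMB) will review all adverse events and all serious adverse events during the whole study period". It then sets out a sequence:

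- The opening review is described thus: "The DMC/DSMB will review all adverse events that may occur after the first two subject have been treated."
- From that review the committee advises whether the study should go on.
- The next pair follows in the text: "The third and fourth subject could be included 1 week after the first two subject have been treated with pedicle screws."
- A second review then takes place, with fresh advice on whether to go on.
- For the remainder of the study the section says: "The DMC/DSMB will have regular meetings to evaluate any kind of events and provide recommendations regarding continuation of the study."

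Section 5.3.3, repeated in the Summary under the number of subjects, gives a minimum wait of one week between the first two subjects and the next two. It mentions the DMC only at the following step. Once subjects one to four have been treated and the DMC's recommendations on continuation are available, the number of subjects treated per day is no longer limited.

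**The concern.** Two things catch the eye.

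First, Section 14 is where a reader looks to learn how the trial can be stopped, and its first sentence denies that any provision exists. Section 13.5, immediately before it, has an independent committee advising on continuation from the second subject onward. A recommendation on continuation is only meaningful if it can be negative. Section 14 nevertheless assigns new or increased risk to the sponsor and investigator, and no visible text says what follows a negative recommendation.

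Second, at the step from subject two to subject three, the only condition written down is the interval of one week. After subject four, by contrast, Section 5.3.3 names the DMC's recommendations expressly. A site working from Section 5.3.3 alone might take the week to be sufficient, while the DMC, working from Section 13.5, might expect its first recommendation to come before subject three.

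If these readings diverged in practice, the clarity of independent oversight would suffer during the earliest uses of an investigational device, in a study that admits 16-year-olds. That makes the question worth asking even though it does not touch the estimate of screw accuracy.

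**Working it through.** No arithmetic applies, and the plan gives no figure to reproduce. The check is a comparison of Sections 5.1, 5.3.3, 6.1, 6.5, 13.5 and 14 and the Summary.

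**Step 1: what Section 14 denies against what Section 13.5 provides.** The denial covers provisions or interim analyses that can result in early termination. Section 13.5 contains no stopping criterion, no boundary and no look at the accuracy endpoint. Its committee reviews adverse events and gives recommendations. A recommendation does not itself end a trial; the party receiving it does. Taken as a statement that no formal stopping rule or interim look is planned, the sentence agrees with Section 13.5. Taken literally, the word *provisions* is wider than that. The wording is loose, but a conflict is not shown.

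**Step 2: the rest of Section 14.** The second sentence ("Any signs of unknown or increased risks for the subjects will be discussed by the sponsor and investigator") has risk weighed for its effect on the investigation. The third says that deviations may *also* be a reason for stopping or suspending a site, which implies that risk is another such reason. Section 5.1 describes a single-centre study, so ending the one site would in practice end the trial. The opening sentence therefore sits awkwardly with its own section, but the section as a whole does allow for stopping.

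**Step 3: does Section 14 remove the DMC's role?** It says that the sponsor and investigator discuss risk. It does not say that nobody else does. Section 13.5 gives the committee its remit over the whole study period, and that remit does not depend on being repeated in the next section. What is missing is a cross-reference.

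**Step 4: the step from subject two to subject three.**

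| Place | Condition before subjects three and four | DMC mentioned for this step |
|---|---|---|
| Summary and Section 5.3.3 | A delay of one week or more | No |
| Section 13.5 | One week after the first two subjects; worded as permission | Yes: review and recommendation come in the sentences just before |

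The delay in the Summary and Section 5.3.3 is a minimum, and Section 13.5 says only that the next two subjects *could* be included. Neither wording makes the interval sufficient on its own. Section 13.5 runs in order: review, recommendation, subjects three and four, review again, recommendation again. The Summary and Section 5.3.3 speak of recommendations in the plural by the time four subjects have been treated, which fits one after each pair. The three places can all be followed together.

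**Step 5: effect on the analysis.** The DMC reviews adverse events, not graded screw placement. Section 6.1 (240 screws) and Section 6.5 (Clopper-Pearson interval, and a clustered interval by subject) involve no interim look at the primary endpoint. Neither reading of Sections 13.5 and 14 changes a planned estimate or interval.

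**Limit of the check.** Outside the revision history, table of contents and abbreviation list, the visible text names the DMC only in the Summary, Section 5.3.3 and Section 13.5. Section 13.3 is redacted and some pages were removed, so they could not be searched.

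**The case for a change.** The strongest case for acting is that the denial is not confined to statistics. It names provisions as well as interim analyses, so reading it as a statement about formal stopping rules supplies a limit that the words lack. The DMC's advisory status also does not answer the practical question of who acts on a recommendation against continuing. And because the plan makes the DMC's view an explicit condition after subject four, its silence after subject two could be taken as deliberate. The remedy would be cheap: a few words and a cross-reference, with no new data or visits.

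Much of this stands as a comment on drafting. The first sentence of Section 14 is too broad, and the section would read better if it pointed to Section 13.5. The relation between the first recommendation and subject three is conveyed by sentence order, without an express condition.

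The step from there to an error does not stand. Nothing in the plan tells anyone to bypass the DMC, ignore its advice or treat the third subject before it has reviewed the first two. The silence in Section 5.3.3 is that of a section on subject numbers, which gives less detail than the section dedicated to the DMC and does not contradict it.

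**Conclusion.** The concern does not call for a change. The two sections are compatible when each is read in full. Section 14 rules out planned stopping rules and interim looks but still contemplates ending the study, and Section 13.5 adds an advisory committee that operates throughout. The step to subject three is covered by the order of events in Section 13.5, with the one-week interval as a minimum.

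What is left is a gap in detail that a sponsor, site and DMC working from the whole plan would fill sensibly. If the protocol is amended for other reasons, the wording of the Summary and Sections 5.3.3, 13.5 and 14 could be aligned then. The content of any such rule is for the sponsor and the DMC.

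The point cannot be expressed as a number. The first part concerns the wording of one sentence and a missing cross-reference; the second concerns a single transition, from subject two to subject three. Sample size, primary analysis and interpretation are untouched.

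The conclusion rests on two assumptions: that DMC recommendations are advisory, as the word suggests, and that the redacted and removed text contains nothing that contradicts Section 13.5.

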15. PUBLICATION POLICY

It is the intention of the investigator and sponsor to submit the clinical investigation data for publication. Prior to submission, claims on intellectual property will be assessed.

This study will also be registered on clinicaltrials.gov before first enrollment.

16. DEFINITIONS AND ABBREVIATIONS

Abbreviations	Explanation of abbreviation
ADE	Adverse Device Effect
AE	Adverse Event
AK	Air Kerma
CBCT	Cone Beam Computed Tomography
CFR	Code Federal Regulations
CI	Confidence Interval
CRF	Case Report Form
DAP	Dose Area Product
DMC/DSMB	Data Monitoring Committee
e-CRF	Electronic Case Report Form
Entry point	The entry point is the point where the instrument (e.g. pedicle screws, screwdrivers, needle) will enter the body. The entry point can be the skin or the vertebrae, dependent on the type of procedure (Minimally invasive surgery or open surgery, respectively).
IFU	Instructions for Use
IM	Intramuscular
ISO	International Organization for Standardization
IV	Intravenous
MEC	Medical Ethic Committee
MDD	Medical Device Directive
OR	Odds Ratio
Placement	The actual position of the screw in the human body
SAE	Serious Adverse Event
SUS	System Usability Scale

IGT systems Best	Clinical Investigation Plan	XCY607-130099
Status: Final	Observational clinical study with Surgical Navigation to plan, position and check instrument placement for spine surgery interventions	2016 Sep 16 Revision: 6.0 Page 38 of 46

USADE	Unanticipated Serious Adverse Device Effect
-------	---

APPENDIX III: USABILITY TESTING BACKGROUND

Usability testing refers to evaluating a device by testing it with representative users. Typically, during a test, participants will try to complete typical tasks while observers watch, listen and takes notes. The goal is to identify any usability problems, collect qualitative and quantitative data and determine the participant's satisfaction with the device. The intent is to improve the usability of devices to reduce use error.

During an usability test, observers will:

- Learn if participants are able to complete specified tasks (such as essential tasks and safety related tasks to measure effectiveness) successfully
- Identify how much effort does it takes to complete specified tasks (efficiency)
- Find out how satisfied participants are with the product
- Identify changes required to improve user performance and satisfaction
- Analyze the performance to see if it meets the usability objectives

System usability scale (SUS)

The SUS is a simple, ten-item attitude Likert scale giving a global view of subjective assessments of usability developed by Brooke, J^{30,31,32,33}. The user needs to provide agreement or disagreement for the 10 statements. (See also Appendix IV: System usability scale) After the appearing of the SUS in literature and once part of the ISO standard ISO 9241 Part 11 it has become an industry standard and has been used for over 25 years to measure usability.

To interpret the SUS score, it is converted to a percentile rank through a process called normalizing. The graph below shows how the percentile ranks associate with SUS scores and letter grades. For example, a raw SUS score of a 74 converts to a percentile rank of 70%. A SUS score of 74 has higher perceived usability than 74% of all products tested. It can be interpreted as a grade of a B.

Analysis of 500 studies with SUS showed that the average SUS score is a 68. A SUS score above a 68 would be considered above average and anything below 68 is below average.³⁴

[figure not shown]

Figure 9: percentile ranks associated with SUS scores.

³⁰ Bangor, A., Kortum, P.T. and Miller, J.A. (2008) An empirical evaluation of the System Usability Scale (SUS). International Journal of Human-Computer Interaction 24(6). 574–594

APPENDIX IV: SYSTEM USABILITY SCALE

Instruction: Please fill in this questionnaire, which asks you to indicate whether you agree or disagree with ten statements. You don't need to take a lot of time thinking about each question, just give your first impression. If you can't answer a particular question, please mark the center point.

Date of completion:	  /    /    
	Example: 05 / Jan / 2016
Initials of person:	
Function:	 Physician  Technician
How many spine procedures do you perform on average per month?	_____ Months
How many years of experience do you have with the Allura?	_____ Years
How many interventions with Surgical Navigation did you approximately perform?	Total of : _____ procedures with Surgical Navigation
Age range (Years):	 20-39  40-59  60 and above

Please indicate how much you disagree or agree with the following statements:

	Strongly Disagree				Strongly Agree
1. I think that I would like to use this system frequently.	1	2	3	4	5
2. I found the system unnecessarily complex.	1	2	3	4	5
3. I thought the system was easy to use.	1	2	3	4	5
4. I think that I would need the support of a technical person to be able to use this system.	1	2	3	4	5
5. I found the various functions in the system were well integrated.	1	2	3	4	5
6. I thought there was too much inconsistency in this system.	1	2	3	4	5
7. I imagine that most people would learn to use this system very quickly.	1	2	3	4	5
8. I found the system very awkward/cumbersome to use.	1	2	3	4	5
9. I felt very confident using the system.	1	2	3	4	5
10. I needed to learn a lot of things before I could get going with this system.	1	2	3	4	5

IGT systems Best Status: Final	Clinical Investigation Plan Observational clinical study with Surgical Navigation to plan, position and check instrument placement for spine surgery interventions	XCY607-130099 2016 Sep 16 Revision: 6.0 Page 46 of 46
--	---	--

APPENDIX V: BACKGROUND INFORMATION PRIMARY OBJECTIVE

The classification system used in this study is as follows:

- grade 0 = breach 0 mm
- grade 1 = lumbar and thoracic < 2 mm, cervical <1 mm breach distance
- grade 2 = lumbar and thoracic 2-4 mm, cervical 1-2 mm breach distance
- grade 3 = lumbar and thoracic > 4 mm, cervical >2 mm breach distance

This classification system describes the distance of breach. This is measured according to an adapted version of the in literature reported classification method by Gerztbein. This classification system is used for lumbar and thoracic region and is for this study adapted to also include the distance of the breach for pedicles placed in the cervical area.

Furthermore the direction of perforation is interesting to measure (lateral or medial breach), since the consequences of the breach in a different direction might lead to different complications. Therefore additional information will be collected to report on the direction of perforation.

Additionally, the distance between the planned path and the longitudinal axis of the screw indicate how accurate the pedicle screw can be placed according to the planned path. When using the distance between planned path and longitudinal axis of the screw in smallest area of the pedicle (mm), one measures at the most critical point in the pedicle. When measuring the distance between screw tip of the screw and the planned target of screw (mm), this is measured at the somewhat less critical point at the point of the screw.
